Community mass drug administration of antimicrobials has been shown to reduce child mortality in SSA. The mass drug administration of azithromycin to communities in Ethiopia with endemic trachoma was recently shown to reduce mortality among children 1-9 years of age by almost half (49%).[10, 11] Child mortality in these communities was largely due to infectious causes, including malaria, fever, diarrhea or respiratory infection.[10] In another study, a single oral dose of azithromycin provided to children in the context of trachoma control resulted in an 80% reduction in infectious mortality among children 1-5 years of age.[11] Single-dose community-administered azithromycin was associated with decreased mortality over one year of follow-up. Although the mechanism for this observation is not well defined, the broad-spectrum antibiotic coverage and potential effect on pathogen carriage suggest potential benefit in children at risk of re-hospitalization or death.

Mass administration of azithromycin leads to the rapid emergence of widespread macrolide resistance within communities. In a randomized comparison of resistance in nasopharyngeal pneumococcus isolates, communities randomized to azithromycin had increased resistance at 12 months (46.9%) compared to those receiving no azithromycin (9.2%). However, administration of azithromycin did not increase resistance to clindamycin, penicillin, or tetracycline.[48] Although resistance to azithromycin among pneumococcal isolates appears to subside when treatment programs are stopped, the potential impact of community-wide antibiotic administration on prevalence of resistance and treatment failure is of concern.[49, 50] The risk of developing resistance is lower with targeted administration of antibiotics than with community-wide administration. By targeting subgroups of high-risk individuals for empiric antibiotic administration, such as children recently discharged from hospital, the risk of community level resistance can be reduced considerably.

JUSTIFICATION

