To determine the number of children needed to evaluate the effect of azithromycin on biomarkers of enteric inflammation children in the **Enteric Function Cohort**, we assumed an alpha level of 0.05, power of 0.80, and a ratio of treatment to placebo of 1:1. For the outcome of enteric inflammation, and assuming a clinically relevant unit mean difference of 2.8mg/L, and a standard deviation of 7.8mg/L, 250 individuals would need to be enrolled to achieve adequate power to detect associations between the intervention groups.[56, 57] We will enroll 300 children (150 per arm) in this cohort in order to account for 20% potential loss to follow-up.

*Aim 2b. To determine whether empiric administration of azithromycin at hospital discharge increases risk of antimicrobial resistance in commensal *Escherichia coli* (*E. coli*) and pneumococcal isolates from treated children and their household contacts.* We will select a random selection of 400 *E. coli* and 400 *S. pneumoniae* isolates (200 per arm) for β -lactam and macrolide resistance testing. We will also store all *S. pneumoniae*, *E. coli* isolates and other isolated bacteria from stool for potential future testing in the event that resistance prevalence is lower than expected. As shown in Table 7, we will have > 80% power to detect prevalence ratios > 1.1, with an ability to detect the smallest effect sizes when the prevalence of resistance in the placebo group is highest.

While we expect that all 300 adults in the Contact Cohort will have *E. coli* isolated and available for resistance testing, ranges for adult *S. pneumoniae* carriage in Sub-Saharan Africa range from 5-55%. Therefore, we expect 15 to 165 *S. pneumoniae* isolates to be available for resistance testing.[51, 58, 59] Assuming an alpha of .05, a 1:1 ratio of testable isolates, and a prevalence of resistance of 50% in the placebo arm, we will have 80% power to detect a 1.4-fold higher prevalence to 1.9-fold higher resistance prevalence in the contacts of azithromycin-treated children.

Aim 3. To identify correlates and intermediate markers of post-discharge mortality and hospital readmission among hospitalized children.

Conservatively estimating a 20% loss-to-follow-up rate in the RCT and a cumulative incidence of death or re-hospitalization of 22.5%, we will have >80% power to detect hazard ratios ≥ 1.3 between correlates and the outcome with exposure prevalence of $\geq 20\%$ or more and hazard ratios ≥ 1.5 for exposure prevalence <20%.

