Table 7. Power (%) to detect prevalence ratios of macrolide and β -lactamase resistance in 200 *E. coli* and 200 *S. pneumoniae* isolates per treatment group

Resistance Prevalence (%)	Resistance prevalence (%) in placebo group						
	10	20	30	40	50	60	70
10							
20	80						
30	>99	64					
40	>99	99	55				
50	>99	>99	98	48			
60	>99	>99	>99	>99	52		
70	>99	>99	>99	>99	98	55	
80	>99	>99	>99	>99	>99	99	64

PROCEDURES

Recruitment

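### Aim 2b claims more than 80% power for prevalence ratios above 1.1, but six of the 28 cells in its own Table 7 print 48-64%; the 1.9-fold claim for contacts also fails with 15 isolates in total.

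*Protocol*

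**What the plan says.** The Protocol's Sample Size section for Aim 2b plans resistance testing on 400 *E. coli* and 400 *S. pneumoniae* isolates from children, 200 per arm for each organism. It then states: "As shown in Table 7, we will have > 80% power to detect prevalence ratios > 1.1". It adds that the smallest effects are detectable where placebo resistance is highest.

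Table 7 gives power for placebo resistance of 10-70% (columns) against comparison resistance of 20-80% (rows). The row for 50% reads "50 >99 >99 98 48", so 40% against 50% has 48% power.

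For adult contacts, the same section applies a carriage range of 5-55% to all 300 adults: "Therefore, we expect 15 to 165" *S. pneumoniae* isolates. With alpha 0.05, a 1:1 split and 50% resistance in the placebo arm, it claims: "we will have 80% power to detect a 1.4-fold higher prevalence to 1.9-fold higher resistance prevalence in the contacts of azithromycin-treated children".

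The SAP gives no power statement for Aim 2b. Its Sample size section refers to the protocol for further details, so the protocol's statements stand.

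**The concern.** The sentence cites Table 7 as its evidence, and the table contradicts it. Separately, the contact isolates are counted over both arms, so the low end leaves 7 or 8 per arm. That is very few to reach 80% power for any comparison of proportions.

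Resistance is the harm question of this trial. A reader told that ratios just above 1.1 are detectable could take a null result as ruling out small increases. In fact the design has roughly even odds of missing an increase of 10 percentage points across most of the tabulated range.

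**Working it through.** **Inputs.** 200 isolates per arm (Protocol, Sample Size, Aim 2b); two-sided 5% tests (SAP Section 4); 300 contacts, 5-55% carriage, 50% placebo resistance and a 1:1 split (Protocol, Sample Size, Aim 2b).

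**Formula.** For two proportions with the pooled normal approximation:

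power = Φ[(|p2 − p1| − 1.96·s0) / s1]

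where s0 = √[p̄(1 − p̄)(1/n1 + 1/n2)] and s1 = √[p1(1 − p1)/n1 + p2(1 − p2)/n2].

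Example, 30% against 40%: s0 = √(2 × 0.35 × 0.65/200) = 0.0477, and s1 = √((0.21 + 0.24)/200) = 0.0474. Power = Φ[(0.10 − 1.96 × 0.0477)/0.0474] = 55.5%. Table 7 prints 55.

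**Step 1: reproduce Table 7.** It has 7 + 6 + 5 + 4 + 3 + 2 + 1 = 28 filled cells, and 27 reproduce within 2 points. The exception is 40% against 50%, printed 48 and computed 52.0. The six cells below 80% are:

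| Placebo vs azithromycin | Ratio | Printed power | Computed power |
|---|---|---|---|
| 20% vs 30% | 1.50 | 64 | 63.8 |
| 30% vs 40% | 1.33 | 55 | 55.5 |
| 40% vs 50% | 1.25 | 48 | 52.0 |
| 50% vs 60% | 1.20 | 52 | 52.0 |
| 60% vs 70% | 1.17 | 55 | 55.5 |
| 70% vs 80% | 1.14 | 64 | 63.8 |

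The smallest tabulated ratio with at least 80% power is 80/60 = 1.33 (printed 99).

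**Step 2: what 200 per arm can detect.** Solving for the ratio that gives 80% power:

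| Placebo resistance | 10% | 20% | 30% | 40% | 50% | 60% | 70% |
|---|---|---|---|---|---|---|---|
| Detectable ratio | 2.00 | 1.61 | 1.45 | 1.35 | 1.28 | 1.22 | 1.17 |

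The unpooled normal and arcsine methods agree within about 0.01. At a ratio of exactly 1.1, power is 5% at 10% placebo resistance and 35% at 70%. A ratio of 1.1 reaches about 80% only when placebo resistance is around 85% or more, which is outside the table.

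**Step 3: contacts.** 0.05 × 300 = 15 and 0.55 × 300 = 165, both over the two arms together. A 1.9-fold rise from 50% is 50% against 95%.

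| Method | 7 placebo / 8 azithromycin | 8 / 7 | 15 / 15 | Smallest n per arm for 80% |
|---|---|---|---|---|
| Pooled normal | 51.0% | 47.9% | 82.3% | 15 |
| Unpooled normal | 59.7% | 63.6% | 89.2% | 12 |
| Arcsine | 58.1% | 58.1% | 86.6% | 13 |
| Fisher exact | 39.8% | 29.2% | 73.6% | 17 |

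Reaching 80% therefore takes 24-34 isolates in total, which is 8-11% carriage among 300 adults. With 7 to 8 per arm, even the largest possible ratio (2.0, from 50% to 100%) has only about 60-67% power by the pooled normal method.

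At the upper end, 165 in total (82.5 per arm) gives a detectable ratio of 1.42, which fits the stated 1.4. Reading the counts as per arm gives 1.88 for 15 but 1.30 for 165. The stated 1.9 therefore fits a per-arm count and the stated 1.4 a total; neither reading gives both.

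**The case against.** **The base is not settled.** The Protocol's Randomization section can be read as 200 isolates of each organism per visit over both arms. The SAP (Section 6, Outcome Definitions) selects children whether or not an isolate is available, so the number of isolates per arm is not fixed. Replacement ratios could then be as unreliable as the sentence they replace. This stands as a caution. However, these readings only make the detectable ratios larger: at 100 per arm (an assumption), 2.50 at 10% placebo resistance and 1.23 at 70%.

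**The planned analysis differs.** The SAP adjusts secondary aims for multiplicity by Benjamini-Hochberg and specifies GEE models, so an unadjusted two-proportion test is only a planning approximation. That is true, but Table 7 uses the same approximation, and the multiplicity adjustment cannot lower the power needed.

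**Repeat visits might explain 1.9.** Fifteen isolates at each of two follow-up visits make 30, or 15 per arm, with 82% power. The protocol does not say this. It would treat repeat samples as independent, and it does not fit the 1.4 end.

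**The 1.4 end is also slightly short.** Power at exactly 1.40 with 165 isolates is about 75%; the detectable ratio of 1.42 only rounds to 1.4. This is a fair remark, and wording it as approximate is enough.

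**Safeguards and weight.** All isolates are stored so that more can be tested if resistance is lower than expected, and the true powers are visible in the table. Both points limit the consequence. Neither makes the sentence correct.

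**Conclusion.** The concern holds on both counts. At 200 isolates per arm, the detectable ratio is 1.17 to 2.00 across the tabulated range, not just above 1.1. For contacts, 15 isolates in total give 29-64% power for 1.9-fold across the four methods, not 80%. These results assume two-sided 5% tests of two independent proportions and no multiplicity adjustment.

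The one control-group figure the protocol quotes for pneumococcal macrolide resistance is 9.2% (Background; a mass-administration study, so indicative only, and not informative for *E. coli*). At that level the detectable ratio is about 2.05. A contrast as large as the 46.9% against 9.2% quoted there would still have more than 99% power, so the aim itself is not undermined. The error is in the stated power of a secondary aim; the Aim 1 sample size and the primary analysis are untouched. It should be corrected.

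**What to change.** In the Protocol's Sample Size section for Aim 2b:

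1. Replace the claim of ratios above 1.1 with the ratios detectable at 80% power (two-sided 0.05, pooled normal approximation, 200 isolates per arm): 2.00, 1.61, 1.45, 1.35, 1.28, 1.22 and 1.17 at placebo resistance of 10, 20, 30, 40, 50, 60 and 70%. Before finalising, confirm that 200 per arm agrees with the Randomization section and the SAP's selection rule; recompute if it does not.
2. For contacts, keep about 1.4-fold for 165 isolates in total, state that 15 in total is too few for 1.9-fold, and name the method. If 1.9-fold is kept, tie it to about 15 isolates per arm (30 in total, pooled normal).

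Optional, with no effect on the conclusion: in Table 7, 40% against 50% should match its mirror cell, 50% against 60% (52), and 40% against 60% computes to 98 rather than above 99.

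The cost is two reworded sentences. No design change or new data collection is needed.

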Aim 2a. To evaluate possible mechanism(s) by which azithromycin may affect morbidity and mortality, by comparing reasons for re-hospitalization, prevalence of pathogen carriage, and markers of enteric dysfunction between the randomization arms. We calculated the minimum detectable association between treatment arm and cause-specific re-hospitalizations (hospitalization due to diarrhea, acute respiratory infection, malnutrition, or malaria vs. any other) among enrolled children, assuming an alpha level of 0.05, power of 0.80, and a ratio of treatment to placebo of 1:1. Based on data from Kenya, re-hospitalization rates due to specific causes ranged from approximately 0.5% to 5.7% in the 6 month post-discharge period, with the lowest rate reported for gastroenteritis and the highest for malaria.[9] By not conditioning on the child having the same diagnosis at initial hospitalization, we expect the cumulative incidence of cause-specific re-hospitalizations to range from 2.5% to 10%. With this range of outcome rates, we will be able to detect hazard ratios of 0.48 to 0.70 for the effect of azithromycin on specific severe morbidities.

Among the 1400 children in whom nasopharyngeal swabs and stool samples are cultured, we expect 56% of children in the placebo group to have *S. pneumoniae* identified based on data from Kenya, providing $\geq 80\%$ power to detect a prevalence ratio of 0.85 (or 1.15) between the two treatment arms at each time point.[51-53] Because there is a strong link between carriage of *S. Pneumoniae* and development of associated disease, and because empiric azithromycin has been shown to prevent reduce clinical pneumonia by as much as 75% in an outbreak setting, we believe that our ability to detect a 15% reduction in risk is appropriately sensitive.[54, 55] Based on prevalence of *Salmonella* spp., *Shigella* spp., *Campylobacter* spp., or diarrheagenic *E. coli* (ETEC, EHEC, EPEC, and EAEC) among asymptomatic children in Western Kenya, we expect 20% of children in the placebo group to have a bacterial pathogen isolated at each time point, resulting in $\geq 80\%$ power to detect differences in enteric pathogen prevalence of 0.68 (1.36) at each time point.[48]

Figure 6. Power and detectable hazard ratios given a range of mortality rates

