Prevalence of Shigella , Salmonella , Campylobacter , Cryptosporidium , Giardia @ enrollment, day 90, and day 180	Visits that occur within 30-days on either side of 90-days (M3) and 180-days (M6) visits will be included. Therefore, visits occurring outside of 60-120 days post-enrollment for M3 and outside of 150-210 days post enrollment for M6 will be excluded from the primary analysis but included in sensitivity analyses.
Streptococcus pneumoniae (S. pneumoniae) prevalence @ enrollment, day 90, and day 180	Visits that occur within 30-days on either side of 90-days (M3) and 180-days (M6) visits will be included. Therefore, visits occurring outside of 60-120 days post-enrollment for M3 and outside of 150-210 days post enrollment for M6 will be excluded from the primary analysis but included in sensitivity analyses.
Prevalence of resistance to azithromycin in E.coli and S. pneumoniae and prevalence of ESBL-producing E.coli @ enrollment, day 90, and day 180	Visits that occur within 30-days on either side of 90-days (M3) and 180-days (M6) visits will be included. Therefore, visits occurring outside of 60-120 days post-enrollment for M3 and outside of 150-210 days post enrollment for M6 will be excluded from the primary analysis but included in sensitivity analyses.

SECTION 4. STATISTICAL PRINCIPLES

Confidence Intervals and P values

Level of statistical significance

All statistical tests will be 2-sided using a 5% significance level (alpha of 0.05). For the primary aim (aim 1), an alpha of 0.045 will be used for hypothesis tests that were part of the interim analysis to account for alpha spending.

Type I errors

We will not adjust the alpha for multiple testing in the primary aim. Instead we will clearly state primary and secondary analyses and interpret secondary analyses as hypothesis-generating rather than confirmatory. All secondary aims will be adjusted for multiple comparisons using the Benjamini and Hochberg method using a false discovery proportion of 0.05.

Confidence intervals to be reported

For the primary analysis of Aim 1, two-sided 95.5% confidence intervals will be used to account for the 0.045 alpha spent at the interim analysis. All other analyses will utilize two-sided 95% confidence intervals.

Adherence and Protocol Deviations

Definition of adherence to intervention and how this is assessed including extent of exposure

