Outcome	Azithromycin-treated group (N=)			Placebo-treated group (N=)			Effect Estimate		
	n	Person-time	Incidence rate (/100)	n	Person-time	Incidence rate (/100)	Hazard ratio	(95% CI)	p-value
Death or re-hospitalization									

In subgroup analyses, we will compare treatment effects in children whose caregivers report no additional antibiotic use over follow-up and separately, who report no additional azithromycin use specifically and in subsets of children defined by the following baseline characteristics: age, county of recruitment, HIV-exposure status, nutritional status, and discharge diagnosis. We will not conduct formal testing of interaction in these analyses. We will report within sub-group p-values but interpret as secondary sub-group analyses. Also in secondary analyses, we will allow more than one hospitalization and model the incidence of re-hospitalization by randomization arm using Anderson-Gill models.

We will report causes of death (and predisposing conditions in those deaths) by randomization arm (without statistical testing) as presented in Table 4.

Table 4. Causes of death by randomization arm

	Azithromycin-treated group (N=)	Placebo-treated group (N=)
Primary cause		
LRTI/Pneumonia		
Diarrhea		
Malaria		
Tuberculosis		
Other Infection		
Other non-infectious		
Predisposing conditions		
HIV		
Sickle cell disease		
Confirmed acquired condition		
Confirmed congenital condition		
None		

Statistical Analysis of Secondary Aims

In addition to the primary aim of the study to determine whether a short-course of azithromycin reduces risk of post-discharge morbidity and mortality, secondary aims include determining potential mechanisms and intermediate markers of an intervention effect, the impact of the antibiotic course on antimicrobial resistance in gut and nasopharyngeal pathogens, and correlates of post-discharge morbidity and mortality. The below tables outline these planned analyses.

Aim 2a. To evaluate possible mechanism(s) by which azithromycin may affect morbidity and mortality, by comparing reasons for re-hospitalization and prevalence of pathogens between the randomization arms.

Population	Dependent variable	Independent Variable	Covariates	Statistical model
------------	--------------------	----------------------	------------	-------------------

Reasons for re-hospitalization				

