1. Randomly selected adult contacts who are participating in AMR sub-study 2. Random subset of adult AMR sub-study participants in whom S. pneumoniae	Prevalence of resistance to azithromycin. In secondary analyses, prevalence of amoxicillin/ K clavulanate, ampicillin, chloramphenicol, clarithromycin, erythromycin, penicillin, trimethoprim-sulfamethoxazole @ 0, 3, & 6 months	Randomization arm (ITT primary and per-protocol secondary)	1) Site 2) Adjusting for imbalanced baseline factors & baseline presence of resistance 3) Adjusting for propensity score made up of factors predictive of likelihood that S. pneumoniae is isolated	GEE with Poisson link & exchangeable correlation structure. Wald tests to compare between arms and to test for time-interaction (waning in resistance from 3 to 6 months in AZM arm)

Aim 3. To identify correlates and intermediate markers of post-discharge mortality and hospital-readmission among hospitalized Kenyan children.

Population	Dependent variable	Independent Variable(s)	Covariates	Statistical model
All enrolled children	Time to death or re-hospitalization	• Child nutritional status • HIV status (child & mother) • Vaccination status • Abnormal discharge • Discharge diagnosis • Length of hospital admission • Infection presence at discharge • Antibiotic resistance at discharge • Feeding practices • Socio-economic status • Caregiver education and nutritional status	Randomization arm, site	Cox proportional hazards
	Time to re-hospitalization		Randomization arm, site	Cox proportional hazards and Andersen-Gill for >1 hospitalization
	Time to death		Randomization arm, site	Cox proportional hazards

Aim 4. To determine the cost-effectiveness of post-discharge administration of a 5-day course of azithromycin in settings of varying antibiotic use, re-hospitalization rates, and mortality rates.

Costs analysis: We will assess the costs of all supplies, services and equipment necessary to implement the intervention (direct medical costs). The perspective will be that of the healthcare provider, i.e. Kenya's Ministry of Health. Using WHO guidelines and its ingredients approach, we will quantify the resources and associated unit costs required to deliver a 5-day course of azithromycin, organized in Version 5.0

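### Protocol Aim 3 claims more than 80% power for a hazard ratio of 1.3, but its own inputs give 252 events and about 38% to 55% power

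*Protocol*

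**What the plan says.** The Aim 3 paragraph of the protocol's Sample Size section gives its inputs as "Conservatively estimating a 20% loss-to-follow-up rate in the RCT and a cumulative incidence of death or re-hospitalization of 22.5" per cent. From these it claims ">80% power to detect hazard ratios ≥ 1.3 between correlates and the outcome with exposure prevalence of" 20% or more, and also "hazard ratios ≥ 1.5 for exposure prevalence <20" per cent. Planned enrolment, from the Aim 1 paragraph, is 1,400.

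The protocol's Data Analysis section and the SAP's Aim 3 table both plan Cox regression. The SAP (Section 4) sets two-sided 5% tests and adds: "All secondary aims will be adjusted for multiple comparisons using the Benjamini and Hochberg method using a false discovery proportion of 0.05". Section 6 counts "and correlates of post-discharge morbidity and mortality" among the secondary aims. Its Aim 3 table lists 11 groups of correlates, beginning "Child nutritional status • HIV status (child & mother) • Vaccination status • Abnormal discharge • Discharge diagnosis". The SAP does not repeat or correct the Aim 3 power statement.

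**The concern.** The claim conflicts with the protocol's own Aim 1 calculation. That calculation needs 1,100 children to detect a hazard ratio of 0.70 with 80% power under an even split. On the log scale 1.3 is a smaller effect (0.262 against 0.357), and 20% against 80% is a less efficient split than 50% against 50%. A similar number of children at the same incidence cannot then give more than 80% power.

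This paragraph is the only statement of what the correlates aim can detect. A reader who relies on it could take a null result for a correlate with a true hazard ratio near 1.3 as evidence of no association, when such a result was about as likely as not.

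**Working it through.** **Inputs.** 1,400 children (protocol, Sample Size, Aim 1); 20% loss and 22.5% cumulative incidence (Aim 3 paragraph); two-sided alpha 0.05 (SAP Section 4, since the Aim 3 paragraph does not restate it).

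**Formula.** For a binary exposure with prevalence p, events needed for 80% power = (1.96 + 0.8416)² / [p(1−p)(ln HR)²] = 7.849 / [p(1−p)(ln HR)²]. Power with E events = Φ(√(E·p(1−p))·ln HR − 1.96).

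**Check on the plan's own figure.** Aim 1, HR 0.70, p = 0.5: 4 × 7.849 / (ln 0.70)² = 246.8 events. Divided by 0.225, this is 1,097 children, against the 1,100 stated. The formula therefore reproduces the Aim 1 calculation.

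**Events available for Aim 3.** 1,400 × 0.80 = 1,120 children; 1,120 × 0.225 = 252 events. With no loss: 1,400 × 0.225 = 315.

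**Hazard ratio 1.3** (ln 1.3 = 0.2624). The simulation used 1,120 children, exponential times, one binary covariate, a log-rank test and 10,000 runs per prevalence.

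| Prevalence | Events needed | Power, 252 events | Power, 315 events | Simulated, 1,120 children |
|---|---|---|---|---|
| 20% | 713 | 38% | 46% | 43% |
| 30% | 543 | 48% | 57% | 52% |
| 50% | 456 | 55% | 64% | 55% |

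Worked line at 20%: √(252 × 0.16) × 0.2624 − 1.96 = −0.29, and Φ(−0.29) = 0.38. Because p(1−p) peaks at 50%, 456 is the smallest requirement at any prevalence. It corresponds to 456 / 0.225 ≈ 2,027 children followed, or 2,027 / 0.80 ≈ 2,534 enrolled.

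**Hazard ratio 1.5, prevalence below 20%.**

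| Prevalence | Events needed | Power, 252 events | Power, 315 events | Simulated, 1,120 children |
|---|---|---|---|---|
| 19% | 310 | 71% | 81% | 78% |
| 15% | 374 | 63% | 73% | 71% |
| 10% | 530 | 49% | 58% | 58% |

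The formula is somewhat pessimistic at low prevalence, because exposed children contribute more than their share of events. The simulation allows for this.

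**Other readings, hazard ratio 1.3.**
- One-sided 0.05 with 252 events: at most 67%.
- 22.5% taken as the risk in unexposed children, with 20% loss: at most about 60%.
- 1.3 taken as a risk ratio, with 20% loss: 56% at 20% prevalence, 73% at 50%.
- The protocol's upper incidence of 45.5%, which this paragraph does not use: 66% at 20% prevalence.

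Among the variants tried, the only one above 80% at 20% prevalence counts all 1,120 children as events (94%). That may be how the figure arose, but the documents do not show the calculation.

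**What 252 events can detect with 80% power.** exp(2.8016 / √(252·p(1−p))) = 1.80, 1.55, 1.47 and 1.42 at 10%, 20%, 30% and 50%. Simulated values are slightly lower for rarer exposures (about 1.7, 1.51 and 1.45 at 10%, 20% and 30%) and the same at 50%.

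**Related point, Aim 2a.** The protocol says "we expect the cumulative incidence of cause-specific re-hospitalizations to range from 2.5% to 10" per cent and then "With this range of outcome rates, we will be able to detect hazard ratios of 0.48 to 0.70 for the effect of azithromycin". By the same formula, HR 0.48 needs about 58 events and HR 0.70 about 247. First events in 1,120 to 1,400 children would number 28 to 35 at 2.5% and 112 to 140 at 10%. The planned Andersen-Gill model also counts repeat admissions, so this range is not shown to be wrong. It cannot be reproduced, because that paragraph gives no loss rate or recurrence rate and does not say whether the rates are overall or placebo-arm rates.

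**The case against.** The arithmetic for hazard ratio 1.3 has no good rebuttal. The objections concern scope and consequence.

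- *The 55% ceiling depends on the reading.* This is true. It takes 22.5% as the overall incidence, full 20% loss and two-sided testing. Children lost part-way contribute some person-time, so events could lie between 252 and 315. Every reading that keeps 20% loss and 22.5% incidence still falls short of 80%.
- *The SAP already limits the harm.* This largely stands. Section 4 treats secondary analyses as hypothesis-generating and requires 95% confidence intervals, which show what a null result excludes. No decision rule uses the power sentence. That is why the point is minor.
- *Hazard ratio 1.5 is nearly met close to 20% prevalence.* This is also true: 78% by simulation at 19%. But the claim has no lower limit on prevalence, and at 10% it clearly fails.
- *Some correlates may be analysed as continuous.* For a hazard ratio of 1.3 per standard deviation, 252 events would give Φ(√252 × 0.2624 − 1.96) = 99% power. The sentence, however, is framed in terms of exposure prevalence, so it concerns binary exposures.
- *Aim 2a is not proven wrong.* Agreed. It is a request for missing inputs, and the Aim 3 conclusion does not depend on it.

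**Conclusion.** The Aim 3 power statement is wrong as written. On its own inputs, power for a hazard ratio of 1.3 is about 38% to 55% by formula (43% to 55% by simulation) across prevalences from 20% to 50%, not above 80%. The hazard ratio 1.5 statement fails for exposures well below 20% and narrowly misses just under 20%.

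These figures assume a single binary exposure, 22.5% overall incidence and unadjusted two-sided alpha 0.05. Adjustment for correlated covariates and the planned Benjamini-Hochberg procedure would both lower power further. Severity is minor, because the error is confined to interpreting a secondary aim. Confidence is high for Aim 3 and moderate for the Aim 2a remark, which depends on inputs the protocol does not state.

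**What to change.** Replace the Aim 3 power sentence in the protocol, or add a note to the SAP, along these lines: with 20% loss and 22.5% incidence (252 events), 80% power is reached by the standard event formula for hazard ratios of about 1.80, 1.55, 1.47 and 1.42 at exposure prevalences of 10%, 20%, 30% and 50%, at unadjusted two-sided alpha 0.05. With no loss (315 events) the corresponding values are 1.69, 1.48, 1.41 and 1.37.

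Add that the false-discovery adjustment makes the detectable hazard ratios somewhat larger. The SAP does not define the family of tests. If the 11 listed correlate groups were one family with one test each (an assumption), the strictest step would be 0.05/11 = 0.0045, and the detectable values at 252 events would rise to at most about 1.79 at 20% prevalence and 1.59 at 50%.

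For Aim 2a, state the number of children after loss, whether 2.5% to 10% are overall or placebo-arm rates, and the recurrence rate that supports the quoted hazard ratios.

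The cost is wording only. Sample size, data collection and analyses stay as they are; the stated sensitivity of the secondary aims becomes less favourable.
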